Cognitive Interviewing Probes – Instructions

Did you have any problems in understanding the instructions? If so, please describe these problems.

Below is a list of statements that other people diagnosed with anal HSIL and treated or actively monitored have said are important. Please check the box to select your answer based on your experiences in the past 7 days.

What does the word experiences mean to you as it is used in these instructions? Is there another word or phrase that you would prefer that we use?

Cognitive Interviewing Probes – Question-Specific

You were asked about PAIN as a possible symptom related to your Anal HSIL. Do you experience PAIN that is separate from ANAL PAIN or PAIN DURING BOWEL MOVEMENTS?

If so, how is the PAIN you experience different from ANAL PAIN or PAIN DURING BOWEL MOVEMENTS? Do you believe we should ask about all three types of PAIN?

What does ITCHING IN OR AROUND THE ANUS mean to you as it was used in this statement? Do you feel that ITCHING IN and ITCHING AROUND should be two separate statements?

If patient experiences DISCHARGE (WETNESS):

Which of the words DISCHARGE (WETNESS) do you prefer to describe this experience? Is there another word or phrase that you feel would better describe this experience?

What does BURNING SENSATION mean to you as it was used in this statement? Is there another word or phrase that you feel would better describe this experience?

What does PHYSICAL ABILITY TO MOVE AROUND mean to you as it was used in this statement? Is there another word or phrase that you feel would better describe this experience? If you were to choose between “moverse” and “movilizarse,” which word would you prefer?

What does PROBLEMS WITH SITTING mean to you as it was used in this statement? Is there another word or phrase that you feel would better describe this experience? Would you prefer that we use “difficulty” sitting?

What does DAILY HOUSEHOLD CHORES (CLEANING, COOKING, LAUNDRY, HOUSE MAINTENANCE) mean to you as it was used in this statement? Are there other examples that you feel would be better to describe this experience?

What does PROBLEMS TAKING CARE OF MYSELF (BATHING, DRESSING, SHAVING, ETC.) mean to you as it was used in this statement? Are there other examples that you feel would be better to describe this experience?

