12. Tengo problemas terminando las tareas de la casa (por ej., limpiar, cocinar, hacer la colada, llevar la casa)							

13. Tengo problemas con mi arreglo personal diario (por ej., bañándome, vistiéndome, afeitándome)							
14. Tengo problemas participando en actividades de ocio (por ej., mirar televisión, relajarme)							
15. Tengo problemas participando en actividades sociales (por ej., salir a comer, visitar amigos)							
16. Tengo problemas siendo productivo en el trabajo							
SÍNTOMAS PSICOLÓGICOS	Escoja si no aplica	Para nada 0	Un poco 1	Algo 2	Bastante 3	Muchísimo 4	Difícil de entender
17. Tengo dificultad concentrándome							
18. Me ha disminuido el placer de la actividad sexual anal							
19. Me ha disminuido el placer de cualquier forma de actividad sexual diferente a la actividad sexual anal							
20. Me ha disminuido el deseo por la actividad sexual anal							
21. Me ha disminuido el deseo por formas de actividad sexual diferentes a la actividad sexual anal							
22. Me preocupa que mi enfermedad empeore							
23. Tengo ansiedad							
24. Tengo depresión							
25. Tengo problemas con mis relaciones íntimas							

Ahora nos va a contar cuáles fueron sus respuestas para cada una de las 25 preguntas (REGISTRE LAS RESPUESTAS EN SU FORMULARIO). Por favor cuénteme si escogió “Difícil de entender” o “No aplica”.

Sondeo de la entrevista cognitiva – General

Primero, para las cosas que contestó, fue fácil de contestar....

- Todo el tiempo
- La mayoría del tiempo
- Algunas veces
- Nunca

¿Hubo algún problema que hizo difícil contestar la encuesta en general? Si sí, ¿qué?

Ahora examinemos lo que le pareció difícil de entender. Olvidándose de las cosas que ya me ha contado, ¿cuáles fueron los problemas que surgieron en esos momentos?

(Algunos de los asuntos planteados durante esta porción podrían hacer resaltar problemas específicos que forman parte de nuestro objetivo. Por favor tome nota de ellos para que no vuelvan a surgir durante la entrevista).

Sondeo de la entrevista cognitiva – Instrucciones

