¿Tuvo algún problema entendiendo las instrucciones? Si sí, por favor describa estos problemas.

*A continuación presentamos una lista de afirmaciones que otras personas diagnosticadas con HSIL (lesión precancerosa en el ano) y que han sido tratadas o monitoreadas activamente han dicho que son importantes. Por favor seleccione la casilla con su respuesta basándose en sus experiencias **en los últimos 7 días**.*

¿Qué significa para usted la palabra “experiencias” tal como se utiliza en estas instrucciones?
¿Preferiría que utilicemos alguna otra palabra o frase?

Sondeo de la entrevista cognitiva – Preguntas específicas

Le preguntaron sobre DOLOR como un síntoma posible relacionado con HSIL anal.

¿Experimenta DOLOR no vinculado con el DOLOR ANAL o DOLOR DURANTE LA DEFECACIÓN?

Si respondió que sí, ¿el DOLOR que usted siente es diferente al DOLOR ANAL o DOLOR DURANTE LA DEFECACIÓN? ¿Le parece que debemos preguntar sobre los tres tipos de DOLOR?

¿Qué quiere decir para usted PICAZÓN EN EL ANO O ALREDEDOR DEL ANO según se preguntó en esta afirmación? ¿Piensa que PICAZÓN EN y PICAZÓN ALREDEDOR deberían ser dos afirmaciones separadas?

Si el paciente experimenta SECRECIÓN (MOJADO):

¿Cuál palabra SECRECIÓN (MOJADO) prefiere para describir esta experiencia? ¿Existe otra palabra o frase que piensa que describiría mejor esta experiencia?

¿Qué significa para usted SENSACIÓN DE ARDOR según se usó en esta afirmación? ¿Existe otra palabra o frase que piensa que describiría mejor esta experiencia?

¿Qué significa para usted LA CAPACIDAD FÍSICA PARA MOVILIZARSE en esta afirmación? ¿Existe otra palabra o frase que piensa que describiría mejor esta experiencia? Si tuviera que elegir entre “moverse” o “movilizarse”, ¿cuál palabra elegiría?

¿Qué significa para usted TENER PROBLEMAS PARA SENTARSE en esta afirmación? ¿Existe otra palabra o frase que piensa que describiría mejor esta experiencia? ¿Preferiría que se usara la frase “dificultad para sentarse”?

¿Qué significa para usted TAREAS DE LA CASA DIARIAS (LIMPIAR, COCINAR, HACER LA COLADA, LLEVAR LA CASA) según se usó en esta afirmación? ¿Hay otros ejemplos que piensa que funcionarían mejor para describir esta experiencia?

¿Qué significa para usted PROBLEMAS PERSONALES DIARIOS (BAÑÁNDOSE, VISTIÉNDOSE, AFEITÁNDOSE, ETC.) según se usó en esta afirmación? ¿Hay otros ejemplos que piensa que funcionarían mejor para describir esta experiencia?

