APPENDIX XI: ANCHOR HEALTH-RELATED SYMPTOM INDEX – ENGLISH

Below is a list of statements that other people diagnosed with anal HSIL (pre-cancer lesion in the anus) and treated or actively monitored have said are important. Please check the box to select your answer based on your experiences in **the past 7 days**.

PHYSICAL SYMPTOMS	Check if Not Applicable	Not at all 0	A little bit 1	Somewhat 2	Quite a bit 3	Very much 4	Difficult to Understand
1. I have anal pain							
2. I have pain other than anal pain							
3. I have pain during bowel movements							
4. I have constipation							
5. I have bleeding from the anus							
6. I have itching in or around the anus							
7. I have discharge (wetness) in my anal area							
8. I have burning sensations in the anal area							
9. I have urgency for bowel movements							
PHYSICAL IMPACTS	Check if Not Applicable	Not at all 0	A little bit 1	Somewhat 2	Quite a bit 3	Very much 4	Difficult to Understand
10. I have problems with my physical ability to move around							
11. I have problems with sitting							
12. I have problems completing daily household chores (e.g., cleaning, cooking, laundry, house maintenance)							
13. I have problems taking care of myself (e.g., bathing, dressing, shaving)							
14. I have problems participating in leisure activities (e.g., watching television, relaxing)							

15. I have problems participating in social activities (e.g., going out to eat, visiting friends)							
16. I have problems with work productivity							
PSYCHOLOGICAL SYMPTOMS	Check if Not Applicable	Not at all 0	A little bit 1	Somewhat 2	Quite a bit 3	Very much 4	Difficult to Understand
17. I have difficulty concentrating							
18. I have a decreased enjoyment of anal sexual activity							
19. I have a decreased enjoyment for any form of sexual activity other than anal sexual activity							
20. I have a decreased desire for anal sexual activity							
21. I have decreased desire for forms of sexual activity other than anal sexual activity							
22. I am worried about my condition getting worse							
23. I have anxiety							
24. I have depression							
25. I have problems with my intimate relationships							

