APPENDIX XII: ANCHOR HEALTH-RELATED SYMPTOM INDEX – SPANISH

ÍNDICE DE SÍNTOMAS RELACIONADOS CON LA SALUD ANCHOR

A continuación presentamos una lista de afirmaciones que otras personas diagnosticadas con HSIL (lesión precancerosa en el ano) y que han sido tratadas o monitoreadas activamente han dicho que son importantes. Por favor seleccione la casilla con su respuesta basándose en sus experiencias en **los últimos 7 días**.

SÍNTOMAS FÍSICOS	Escoja si no aplica	Para nada 0	Un poco 1	Algo 2	Bastante 3	Muchísimo 4	Difícil de entender
1. Tengo dolor anal							
2. Tengo dolor pero no en el área anal							
3. Tengo dolor cuando entro al baño a defecar							
4. Tengo estreñimiento							
5. Tengo sangrado del ano							
6. Tengo picazón en el ano o alrededor del ano							
7. Tengo una secreción (mojado) en el área anal							
8. Tengo sensación de ardor en el área anal							
9. Siento urgencia de entrar al baño a defecar							
IMPACTOS FÍSICOS	Escoja si no aplica	Para nada 0	Un poco 1	Algo 2	Bastante 3	Muchísimo 4	Difícil de entender
10. Tengo problemas con mi capacidad física para movilizarme							
11. Tengo problemas para sentarme							
12. Tengo problemas terminando las tareas de la casa (por ej., limpiar, cocinar, hacer la colada, administrar la casa)							
13. Tengo problemas con mi arreglo personal diario (por ej., bañándome, vistiéndome, afeitándome)							
14. Tengo problemas participando en actividades de ocio (por ej., mirar televisión, relajarme)							

15. Tengo problemas participando en actividades sociales (por ej., salir a comer, visitar amigos)							
16. Tengo problemas siendo productivo en el trabajo							
SÍNTOMAS PSICOLÓGICOS	Escoja si no aplica	Para nada 0	Un poco 1	Algo 2	Bastante 3	Muchísimo 4	Difícil de entender
17. Tengo dificultad concentrándome							
18. Me ha disminuido el placer de la actividad sexual anal							
19. Me ha disminuido el placer de cualquier forma de actividad sexual diferente a la actividad sexual anal							
20. Me ha disminuido el deseo por la actividad sexual anal							
21. Me ha disminuido el deseo por formas de actividad sexual diferentes a la actividad sexual anal							
22. Me preocupa que mi enfermedad empeore							

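### The Spanish script's item 13 probe asks about a phrase the item does not contain, and item 12 has two Spanish wordings: a minor fault, local to these two items

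*Protocol*

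**What the plan says.** Protocol Sections 2.3 and 4.0 give the purpose of the Spanish interviews as establishing the content validity of the Spanish measure, and point to Appendix XII for its text. The Spanish script is Appendix VIII. It contains a 25-item grid, which the participant answers, followed by scripted probes.

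**Item 13.** The Appendix VIII grid prints "Tengo problemas con mi arreglo personal diario (por ej., bañándome, vistiéndome, afeitándome". Appendix XII prints the same item, beginning "Tengo problemas con mi arreglo personal diario". The probe asks what "PROBLEMAS PERSONALES DIARIOS (BAÑÁNDOSE, VISTIÉNDOSE, AFEITÁNDOSE, ETC" means to the participant as used in the statement. In English, the item begins "I have problems taking care of myself" (Appendix XI) and the probe asks about "PROBLEMS TAKING CARE OF MYSELF (BATHING, DRESSING, SHAVING, ETC" (Appendix VII).

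**Item 12.** The Appendix VIII grid prints "Tengo problemas terminando las tareas de la casa (por ej., limpiar, cocinar, hacer la colada, llevar la casa" and the probe asks about "TAREAS DE LA CASA DIARIAS (LIMPIAR, COCINAR, HACER LA COLADA, LLEVAR LA CASA". Appendix XII has the same item except for the verb in the last example, which is *administrar* instead of *llevar*. English item 12 speaks of daily chores; neither Spanish grid carries that qualifier.

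The item 12 and item 13 probes share one follow-up: "Hay otros ejemplos que piensa que funcionarían mejor para describir esta experiencia".

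**The concern.** In a cognitive interview study the script is the measuring instrument. A meaning probe shows whether respondents understand an item as its authors intend, but only if it puts the item's own words to them. At item 13 it does not.

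The item needs that test. The Spanish is not a literal rendering of the English: it speaks of daily grooming or personal care where the English speaks of taking care of oneself, and it adds a daily qualifier that the English lacks. Whether Spanish speakers read it as intended is the question these interviews exist to answer.

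At item 12 the document holds two versions of one item. The probe follows one of them and adds a word found in neither. Asking about daily chores could hide the fact that the Spanish item omits the qualifier.

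**Working it through.** No statistical figure is at issue, and Section 5.0 says no formal analysis plan is required. The check is a comparison of texts.

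**1. Spanish grid against Spanish grid (Appendix VIII against XII).** Of 25 items, 1 differs (item 12, one verb in one of four examples), so 25 − 1 = 24 agree. All 5 response labels agree.

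**2. Spanish probes against Spanish items.** Appendix VIII has 14 probes that ask what an item's wording means (items 6, 8, 10 to 18, 20, 22 and 25). I compared each with its item by word root, allowing for inflection.

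| Item | Printed in the Spanish grids | Put to the participant in the probe | Result |
|---|---|---|---|
| 13 | noun *arreglo*, with *personal diario* | *arreglo* absent; adjectives made plural to agree with *problemas* | key word lost, meaning changed |
| 12 | no *diarias*; last example *llevar* (VIII) or *administrar* (XII) | *diarias* added; *llevar* | one added word; matches one of two versions |
| 16 | *productivo* | *productividad* | same root, meaning kept |
| 22 | *preocupa* | *preocupado* | same root, meaning kept |

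Item 13 is the only probe that loses its item's key word, so 14 − 1 = 13 keep it. What counts as the key word is a judgement. Several probes, in both languages, also leave out the lead-in about having problems; item 12 is an example.

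**3. Is it a reading error from the PDF?** No. The adjectives in the item 13 probe agree in the plural with *problemas*. The phrase is complete as written; a word has not simply fallen out.

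**4. Is it inherited from English?** No for item 13: the Appendix VII probe repeats its item stem. For item 12, *diarias* mirrors the English item and probe, but the Spanish item itself lacks it.

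**5. What else in the script tests the printed wording?**
- Appendix VI asks participants to have the measure with them at the appointment.
- The item 13 probe keeps the three printed examples and refers back to the statement.
- Each item has a *Difícil de entender* box. The interviewer asks which boxes were ticked and then explores the problems.
- The closing questions ask whether any statement was particularly difficult and invite suggestions.

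These catch a participant who notices a difficulty. They do not reliably catch one who reads item 13 with confidence but in another sense. Only a meaning probe using the item's words does that.

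**6. Reach.** The fault concerns 2 of 25 items. Round 1 plans 20 interviews. Section 2.3 makes Rounds 2 and 3 (up to 10 each) conditional on need, so the ceiling is 20 + 10 + 10 = 40.

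**7. Lesser differences found on the way.** The response-scale probe in Appendix VIII reads out *mucho* where the form prints *Muchísimo* (1 of 5 labels). The follow-up on pain asks in English how the pain differs; in Spanish it asks only whether it differs, which invites yes or no.

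**The case against.** The strongest reply is that little is lost. The participant has just answered the printed item, has it in view, hears the same bathing, dressing and shaving examples, and is asked for the meaning as used in that statement. Many would answer about self-care whatever the probe's label. The interviews are described as semi-structured (Section 7.1), so an interviewer may correct the phrase. Section 3.4.2 rules out transcripts, but Section 7.1 has recordings consulted when each summary is drafted, so a departure from the script can be noted before the recording is deleted. The synopsis also treats Round 1 as feedback on an initial draft, with later rounds available. Nearly all of this stands, and it is why the point is minor. It does not meet the narrow gap: followed as written, the script never asks what item 13's key phrase means.

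A reader might be tempted further in four ways that the documents do not support.
- That content validity of the Spanish index as a whole is in doubt. The grids agree on 24 of 25 items, 13 of 14 meaning probes keep the key wording, and the safeguards above apply to items 12 and 13 too.
- That the follow-up's limitation to other examples is a fault of the Spanish script. The English probes for items 12 and 13 have the same follow-up; it is a shared choice.
- That apart from *diarias* and the one verb, item 12 is probed as printed. The probe also omits the part of the stem about problems completing the chores. The English probe omits it too, so this is no Spanish slip.
- That the absence of transcripts makes any correction untraceable. The use of recordings in drafting summaries answers that in part.

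**Conclusion.** The point holds as a minor text inconsistency in the study's main instrument, confined to two items. At item 13 the scripted meaning probe uses a phrase found in neither Spanish grid, and the item's key phrase is never directly probed. The remaining risk is an undetected confident misreading. At item 12 one of four examples has two Spanish versions, and the probe tests a qualifier the item does not carry. The scale label and the pain follow-up are smaller still: the printed form, the instruction to give examples from the questionnaire and the open question on confusing answer words largely offset the first, and an interviewer can draw out the second.

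This assumes that interviewers read the probes as scripted, and that *arreglo personal* is understood as grooming or personal care, which is my reading of the Spanish. The item 13 point does not depend on which copy the participant holds, since both agree. The item 12 point partly does: Appendix VI does not say which copy is sent, and a participant holding Appendix XII would read *administrar* while being asked about *llevar*. Sample size and accrual are unaffected.

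**What to change.** Before the first interview:

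1. Have the item 13 probe in Appendix VIII quote the item's own phrase, *arreglo personal diario*, with its examples.
2. Use one item 12 wording in the Appendix VIII grid, its probe and Appendix XII. Decide whether *diarias* belongs in the item, as in the English, or should leave the probe.
3. As lesser edits, say *muchísimo* in the response-scale probe, and restore the open question (*cómo* or *en qué*) in the pain follow-up.

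The inflected wording in other probes, such as items 16 and 22, can stay. The cost is a few text edits in Appendix VIII, and in Appendix XII if its item 12 is the copy changed, with whatever amendment step Section 7.2 requires. No participants or procedures are added.

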¿Qué significa para usted PROBLEMAS PARTICIPANDO EN ACTIVIDADES DE OCIO (MIRANDO TELEVISIÓN, RELAJÁNDOSE) según se usó en esta afirmación? ¿Le plantea alguna dificultad la palabra “ocio”? ¿Preferiría que se utilice la frase “actividades que realiza en su tiempo libre”? ¿Hay otros ejemplos que piensa que funcionarían mejor para describir esta experiencia?

¿Qué significa para usted PROBLEMAS PARTICIPANDO EN ACTIVIDADES SOCIALES (SALIR A COMER, VISITAR AMIGOS) según se usó en esta afirmación? ¿Hay otros ejemplos que piensa que funcionarían mejor para describir esta experiencia?

¿Piensa que es importante preguntar sobre ACTIVIDADES DE OCIO y ACTIVIDADES SOCIALES? Si se le preguntara tan solo una de ellas, ¿cuál seleccionaría? ¿Por qué?

¿Qué significa para usted PROBLEMAS CON LA PRODUCTIVIDAD EN EL TRABAJO según se usó en esta afirmación? (PREGUNTE SI EL PARTICIPANTE NO ESTÁ TRABAJANDO) ¿Hay alguna otra palabra o frase que usted cree que describiría mejor esta experiencia?

¿Qué significa para usted DIFICULTAD CONCENTRÁNDOSE según se usó en esta afirmación?

¿Qué significa para usted DISMINUCIÓN DE PLACER DE LA ACTIVIDAD SEXUAL ANAL según se usó en esta afirmación?

¿Preferiría que se utilice la frase “placer físico” en vez de “placer” al preguntar sobre esta experiencia?

¿En qué se diferencia de DISMINUCIÓN DE PLACER POR OTRAS FORMAS DE ACTIVIDAD SEXUAL? ¿Piensa que es necesario que se le pregunte sobre ambos conceptos? Si se le preguntara tan solo uno de ellos, ¿cuál seleccionaría? ¿Por qué?

¿Qué significa para usted DISMINUCIÓN DE DESEO POR ACTIVIDAD SEXUAL ANAL según se usó en esta afirmación?

¿En qué se diferencia de DISMINUCIÓN DE DESEO POR OTRAS FORMAS DE ACTIVIDAD SEXUAL? ¿Piensa que es necesario que se le pregunte sobre ambos conceptos? Si se le preguntara tan solo uno de ellos, ¿cuál seleccionaría? ¿Por qué?

¿Qué significa para usted ESTOY PREOCUPADO QUE MI ENFERMEDAD EMPEORE según se usó en esta pregunta?

¿Qué significa para usted RELACIONES ÍNTIMAS según se usó en esta pregunta?

¿Preferiría que preguntásemos sobre la “intimidad afectiva con otras personas” en vez de “relaciones íntimas”?

Sondeo de la entrevista cognitiva – Comprensión de la escala de respuesta

En general, ¿qué tan difícil fue seleccionar respuestas para las afirmaciones que le pedían que seleccionara, para nada, un poco, algo, bastante, mucho? (DE EJEMPLOS DEL CUESTIONARIO)

- PARA NADA difícil
- UN POCO difícil
- ALGO difícil
- MUY difícil

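### Four of the six scripted wording comparisons (items 11, 14, 18 and 25) are yes/no questions in which 'yes' means reword, so any tendency to agree with the interviewer can bias the evidence toward rewording

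*Protocol*

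**What the plan says.** The question-specific probes in Appendix VIII include six that put named wordings to the participant.

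- Item 7, asked only if the symptom is present: "Cuál palabra SECRECIÓN (MOJADO) prefiere para describir esta experiencia".
- Item 10: "Si tuviera que elegir entre “moverse” o “movilizarse”, ¿cuál palabra elegiría".
- Item 11: "Preferiría que se usara la frase “dificultad para sentarse".
- Item 14: "Preferiría que se utilice la frase “actividades que realiza en su tiempo libre".
- Item 18: "Preferiría que se utilice la frase “placer físico” en vez de “placer” al preguntar sobre esta experiencia".
- Item 25: "Preferiría que preguntásemos sobre la “intimidad afectiva con otras personas” en vez de “relaciones íntimas".

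The English script in Appendix VII uses the same form for each item. Item 7 there reads "Which of the words DISCHARGE (WETNESS) do you prefer to describe this experience" and item 10 reads "If you were to choose between “moverse” and “movilizarse,” which word would you prefer".

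Section 5.0 says that an expert panel will abstract and code the interviews. Sections 2.3 and 4.0 give the purpose as establishing content validity of the Spanish measure. Round 1 has 20 interviews. Section 3.4.2 provides for notes and a summary by the interviewer, no transcripts, and destruction of the recordings within 48 business hours.

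**The concern.** Wording evidence is the main product of this study. In four of the six comparisons the interviewer offers a replacement and asks whether the participant would prefer it. A participant who agrees out of politeness and one who really prefers the new phrase give the same answer, and no scripted follow-up asks for a reason. All four probes lean the same way, so yes-saying adds up across items and does not cancel.

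The stakes are highest for items 18 and 25. Adding 'physical' to the pleasure item narrows it, and the replacement is not offered for its parallel, item 19, so a change would also break that pair. Affective closeness with other people is not the same concept as intimate relationships. A revision prompted by agreement alone would move the Spanish item away from its English counterpart, and Section 7.1 says the final measure goes into the ANCHOR trial.

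**Working it through.** The protocol states no figure on this point, so there is none to reproduce. The main check sets the six probes in Appendix VIII side by side.

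| Item | Form | Current wording named inside the preference question | Item-level open request for other wording | 'Why' asked about the wording |
|---|---|---|---|---|
| 7 | choice between two words | yes (both are in the item) | yes | no |
| 10 | either/or choice | yes | yes | no |
| 11 | yes/no, yes = new phrase | no | yes, just before | no |
| 14 | yes/no, yes = new phrase | no (*ocio* is named in the preceding question) | no (asks only for other examples) | no |
| 18 | yes/no, yes = new phrase | yes | no | no |
| 25 | yes/no, yes = new phrase | yes | no | no |

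This gives three results:

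1. Four of six comparisons are yes/no toward the replacement; two are choices.
2. The scripts already contain a neutral form. Item 10 offers the current word and an alternative on equal terms. The item-pair probes for 14/15, 18/19 and 20/21 ask which one the participant would select, and why.
3. An open probe about meaning comes before each of the four. It shows whether the current wording was understood, but it does not measure preference between two phrases.

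**Illustration only.** Let p be the share who truly prefer the new phrase and a the share who say yes to any suggestion. Neither is in the protocol. Then

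P(yes) = p + (1 − p)a, and the expected excess of yes answers in n interviews is n(1 − p)a.

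With n = 20 (Round 1):

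- p = 0.1, a = 0.1: 20 × (0.1 + 0.9 × 0.1) = 3.8 yes answers, against 2 real.
- p = 0.1, a = 0.3: 20 × (0.1 + 0.9 × 0.3) = 7.4, against 2 real.
- p = 0.2, a = 0.1: 20 × (0.2 + 0.8 × 0.1) = 5.6, against 4 real.
- p = 0.2, a = 0.3: 20 × (0.2 + 0.8 × 0.3) = 8.8, against 4 real.

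The excess is 1.6 to 5.4 answers per item. The share saying yes is 19% to 44%, below half throughout.

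If one also assumes that a majority (11 or more of 20) would count as support, the binomial chance of a majority 'yes' is:

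| True preference p | a = 0 | a = 0.1 | a = 0.2 | a = 0.3 |
|---|---|---|---|---|
| 0.3 | 0.02 | 0.08 | 0.22 | 0.45 |
| 0.4 | 0.13 | 0.28 | 0.48 | 0.69 |
| 0.5 | 0.41 | 0.59 | 0.75 | 0.88 |

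The majority rule is a further assumption. An either/or probe would return the result to the a = 0 column, provided that people who would have said yes to anything then answer by true preference and that alternating the order cancels any order effect.

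**The case against.** The case on the other side has real force.

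- **No decision rule.** Section 5.0 leaves analysis to an expert panel. No vote or threshold is stated, so a reader who infers that these answers decide revision goes beyond the document. They inform it. This stands.
- **Current wording is present.** Items 18 and 25 name it in the same sentence. For item 14, *ocio* appears in the question just before; for item 11, the current phrase opens the probe and an open request for alternatives comes before the suggestion. A reader might call all four probes wholly one-sided, but the text does not support that. What is common to all four is that 'yes' points to the new phrase.
- **Other evidence.** There are meaning probes, a column for items that are hard to understand, general problem probes and closing questions inviting suggestions. These mitigate the problem but do not resolve it. They show whether an item was understood, not which of two phrases is preferred, and without transcripts the panel has only notes and a summary from which to tell agreement from preference.
- **Later rounds.** The synopsis plans to test revised items in a new cohort, and Section 2.3 makes Rounds 2 and 3 conditional on need. That check is useful, but the script gives no reason to expect a neutral probe there.
- **Mixed formats are not an error.** In a qualitative interview this is fair. The protocol contradicts nothing here; the point is a design choice that can be improved.

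**Conclusion.** The concern holds in a limited form. Four of the six wording comparisons use a yes/no question worded toward the replacement, without a 'why', so yes-saying can bias the panel's evidence toward rewording. Only the direction follows from the scripts.

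The size is unknown. A reader might conclude from the illustration that items 11, 14, 18 and 25 will be reworded because of yes-saying. The documents do not support that: the yes-saying rate, the true preference and the majority rule are all assumed, and with true preference of 10% to 20% the expected share saying yes stays below half. The change is worth making because it is small and the scripts already contain the better form, not because a distorted result has been shown.

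**What to change.** In Appendices VII and VIII, put the probes for items 11, 14, 18 and 25 in the form used for item 10, naming both the current and the alternative phrase: 'Si tuviera que elegir entre A y B, ¿cuál elegiría? ¿Por qué?' Alternate the order of A and B from one participant to the next, and have the interviewer record the order used and the reason given, so that both reach the summary report.

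The cost is a short 'why' on four items within a session of about 45 to 60 minutes, and two phrase orders in the script. No further participants or data sources are needed.
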